7. STUDY INTERVENTION

7.1 EchoSure Scan Requirements

The EchoSure scans will be conducted at the vascular surgeon's (investigator's) office/clinic by a member of their staff that does not have formal ultrasound training and has been designated and trained as study personnel. Appropriate staff members to conduct the EchoSure scans include the study research coordinator(s), nurses, nursing assistants, or medical technicians. Prior to starting study activities, each site will designate at least one staff member without previous ultrasound training to conduct the EchoSure scans. These designated EchoSure users will be trained on the use of the EchoSure system and how to fill out the EchoSure case report form, including the blinding of the investigator, during Site Initiation Visits. The designated EchoSure users will be included in the study delegation log of authority and a copy their CV/resume will be included in the site's study regulatory binder. No other study personnel will operate the EchoSure system.

The follow-up EchoSure scans will be conducted by the designated EchoSure user without the investigator and without the sonographer/RVT conducting the Duplex exam in the room, either during the routine work-up prior to the surgeon seeing the patient or after. The EchoSure results for flow, and vessel depth and diameter are shown as numerical values on the screen of the EchoSure device. After each scan, the EchoSure user will transcribe these values onto the case report form. The EchoSure data will not be included elsewhere in the patient's medical record. The CRF data will be entered in to an EchoSure master data spreadsheet by a data manager. This master data spreadsheet will not be available to investigators. While historical EchoSure scans and data are stored on the EchoSure users will be given login credentials. The investigator's will not be provided with login credentials, so they will not be able to log in to the system to conduct EchoSure scans or view any of the EchoSure measurement data.

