7.6 Pre-Maturation Follow-up at 15, 30, 60, 90, 120, 150 Days

Subjects will have follow-up visits at 15 (+/- 7 days), 30 (+/- 7 days), 60 (+/- 15 days), 90 (+/- 15 days), 120 (+/- 15 days), and 150 (+/- 15 days) days from the baseline procedure, including a physical exam, duplex imaging, EchoSure scan, external EchoMark measurement, medical history, and adverse event monitoring. The EchoSure scans will be suspended after the 120 day (4 month) visit or once radiographic maturation is achieved,

whichever is longer. Radiographic maturation is defined as 500mL/min and a 5 mm diameter. The monthly clinical follow-up and duplex imaging will continue per the follow-up schedule. The physical exam will include assessing the fistula for bruit and thrill. The medical history will include all interventions, cannulation history including any attempts, and the most recent Kt/V, CBC, Serum Chemistry, Calcium, Phosphorous, Magnesium, Total Protein, Albumin, PTH. EchoSure scans will be completed by study personnel who do not have prior ultrasound training, are representative of non-expert users, and have been delegated on the delegation of authority log. Duplex and EchoSure scans will include:

- A total of three (3) EchoSure scans performed at the site of the EchoMark. Volume flow, diameter, and depth data to be recorded.
- A total of three (3) limited DUS scans performed at the site of the EchoMark. DUS will be performed in transverse Bmode and longitudinal view. Volume flow, diameter, depth, and distance from scan area to anastomosis will be recorded.
- A total of three (3) limited DUS scans performed at the cannulation zone in transverse Bmode and longitudinal view. Volume flow, diameter, and depth, will be recorded.
- The 9 Duplex images will be de-identified and undergo quality control checks performed by an Independent RVT.
- A duplex exam of the fistula from the EchoMark location and beyond to assess for the presence of stenotic lesions. If a lesion is present, capture and save an image showing a longitudinal view of the fistula segment with the stenosis, note the location of the stenosis in relation to the anastomosis and EchoMark, and track the stenosis as an adverse event.
- A duplex scan of the brachial artery to assess flow and diameter, capture a PW image showing the flow and diameter measurements.

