11.2. Data Analysis Plan

11.2.1 General Principles

All statistical analyses will be performed using Statistical Analysis System (SAS) for Windows (version 9.4, SAS Institute Inc. Cary, NC), STATA (version 16, StataCorp, College Station, TX) or other widely accepted statistical or graphical software. All statistical analysis will be conducted by an independent statistician.

Descriptive statistics will be used to present the data and to summarize results. Discrete variables will be presented using frequency distributions and cross tabulations. Continuous variables will be summarized by presenting the number of observations (N), mean, standard deviation, median, minimum, and maximum values. In general, data for all study subjects combined will be presented. The primary analysis for all baseline characteristics and study outcomes will include all available data for all enrolled subjects. Individual data will be presented in subject listings.

Summaries of the following endpoints present the number and percentage of unique subjects within an event, unless specified otherwise: protocol deviations; subject status; adverse events. Thus, multiple occurrences of the same event are counted only once per subject, unless specified otherwise.

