11.2.8 Analysis of Observational Endpoints

Observational endpoints are defined in Section 4.2.

For discrete endpoints, the number and percentage of subjects with success will be summarized. Descriptive statistics for components of each endpoint will also be provided.

For continuous variables (e.g., volume flow, depth, and diameter), results will be summarized with the with the numbers of observations, means, medians, standard deviations, minimums, and maximums. Change from baseline will be included using these same descriptive statistics.

11.2.8.1 Comparison of EchoSure volume flow, diameter and depth to Duplex values:

The degree of correlation between paired EchoSure values and Duplex values that pass the quality checks by an Independent RVT will be analyzed.

The comparison data points are:

- EchoSure vessel depth at EchoMark vs Duplex vessel depth at EchoMark
- EchoSure vessel diameter at EchoMark vs Duplex vessel diameter at EchoMark
- EchoSure volume flow at EchoMark vs Duplex volume flow at cannulation zone (standard of care)

All Duplex volume flow, depth and diameter data points will undergo quality checks performed by an Independent RVT to qualify for inclusion in the comparison analyses. The quality checks will assess if the Duplex data was collected per protocol and meet defined requirements that ensure a uniform technique.

Duplex volume flow data points that do not pass the quality checks will not be included in the analysis. The paired EchoSure flow values for failing Duplex values will also not be included.

Duplex diameter and depth values that do not pass the quality checks will be corrected by an Independent RVT. The corrected Duplex depth and diameter data points will be included in the analysis along with their paired EchoSure values.

All sites and their sonographers will be trained on the Duplex data collection protocol and quality requirements. Each site will be required to submit a set of images for quality checks by an Independent RVT as a part of site qualification.

Degree of correlation between paired EchoSure values and Duplex values (volumetric flow, vessel diameter, vessel depth, etc.) that pass quality checks will undergo the following analyses:

- Pearson Correlations to assess correlation
- Bland Altman testing using percentages will be used to assess for bias and the limits of agreement
- Distribution of correlation percentage between EchoSure and Duplex values

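### Repeated scans are compared with no subject term, and 11.2.8.1 leaves the unit of pairing open, so pooled r mixes spread between patients with tracking within a patient

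*Combined protocol and SAP*

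**What the plan says.** Section 7.6 sets the scans for each pre-maturation visit: "A total of three (3) EchoSure scans performed at the site of the EchoMark", three Duplex scans at the same place, and "A total of three (3) limited DUS scans performed at the cannulation zone in transverse Bmode and longitudinal view". The visits are days 15, 30, 60, 90 and 120, plus day 150 for patients whose EchoSure scans continue. Table 1 also appears to mark an EchoSure scan at discharge, which section 7.5 does not list. Under section 7.1 the EchoSure scans are done without the sonographer in the room, "either during the routine work-up prior to the surgeon seeing the patient or after".

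Section 11.2.8.1 fixes the quantity and the site of each comparison: depth and diameter at the EchoMark for both methods, and EchoSure flow at the EchoMark against Duplex flow at the cannulation zone. The analyses are Pearson correlation, a distribution of correlation percentage, and agreement: "Bland Altman testing using percentages will be used to assess for bias and the limits of agreement". Duplex flow values that fail the quality check are removed, and "The paired EchoSure flow values for failing Duplex values will also not be included". Section 11.2.8.2 applies the same three analyses to EchoSure depth against a reviewer's depth on the same image.

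Related output is planned. Section 11.2.8 states "Change from baseline will be included using these same descriptive statistics", and section 11.2.1 states "Individual data will be presented in subject listings". Section 11.1 says that any inference is exploratory.

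**The concern.** The readings are nested: scans within visits, visits within patients. Neither section names a subject, visit or replicate term. The two sets of scans in 11.2.8.1 come from separate sessions, so the first EchoSure scan has no natural Duplex partner, and the text does not say whether a pair is one scan with one scan or a visit mean with a visit mean. That the readings would be pooled is an inference from this silence; the plan does not say so outright.

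Three things are at stake.

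- A pooled correlation can be high simply because patients differ from one another, while section 3.1 describes the device as displaying results so that change over time can be followed.
- Any interval that treats all pairs as independent would be too narrow.
- Limits of agreement for one scan and for a mean of three answer different questions.

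These are the only planned comparisons of EchoSure readings with a reference.

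**Working it through.** **Inputs from the documents.** Up to 20 subjects (11.1); five or six visits and three scans per visit (7.6). Nominal pairs: 20 × 5 × 3 = 300 or 20 × 6 × 3 = 360 single scans; 100 or 120 visit means. A discharge scan would add more; failed quality checks and suspended scans would leave fewer. The plan gives no target for r, bias or limits, so there is no figure of its own to reproduce.

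**Assumed inputs.** The documents give no variances. The main set uses log-scale SDs of 0.35 between subjects, 0.15 between visits within a subject and 0.08 between scans (variances 0.1225, 0.0225, 0.0064), with mean flow 800 mL/min. Log Duplex = subject + visit + scan noise. Three devices are compared:

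- A: no tracking and flat (subject + scan noise).
- B: full tracking plus a visit-level error with SD 0.15.
- C: no tracking, but with its own visit-to-visit variation, SD 0.15.

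B's error is deliberately set equal to the within-subject SD, so the limits for A and B tie by construction.

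**Large-sample values, single scans, log scale.**

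- Pooled r: A = 0.1225/√(0.1514 × 0.1289) = 0.88; B = 0.1450/√(0.1514 × 0.1739) = 0.89.
- Within-subject r: A = 0; B = 0.0225/√(0.0289 × 0.0514) = 0.58.
- Limits, A and B: 1.96 × √(0.0225 + 2 × 0.0064) = 0.37. C: 1.96 × √(2 × 0.0225 + 2 × 0.0064) = 0.47.
- Limits for visit means, A and B: 1.96 × √(0.0225 + 2 × 0.0064/3) = 0.32.

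**Simulation, 20 × 5 × 3, mL/min scale, 2,000 trials.** Values are slightly lower than the formulas, as expected on the raw scale with 20 subjects.

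| | A | B | C |
|---|---|---|---|
| Pooled r, scan | 0.85 | 0.87 | 0.77 |
| Within-subject r, scan | 0.00 | 0.56 | 0.00 |
| Within-subject r, visit mean | 0.00 | 0.65 | 0.00 |
| Limits, scan | ±36% | ±36% | ±46% |
| SD of change, mL/min (Duplex about 200) | 58 | about 280 | about 200 |

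In single trials, 95% of pooled r values lie in 0.74–0.93 for A and 0.79–0.93 for B. Within-subject r lies in −0.15 to 0.14 for A and about 0.40 to 0.69 for B.

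**Range over variances.** Four sets (between/within/scan 0.35/0.15/0.08, 0.40/0.20/0.08, 0.30/0.20/0.10, 0.40/0.15/0.10) put 69–88% of true variance between subjects; for example 0.09/(0.09 + 0.04) = 69%. Scan-level pooled r is 0.73–0.86 for A and 0.79–0.87 for B; within-subject r is 0.00 and 0.50–0.61. Holding the total at 0.145 and lowering the between-subject share to 50% or 30% brings A's pooled r down to about 0.63 or 0.47.

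**Interval for bias, if one is reported.** Let shares p_s, p_v, p_e of the difference variance lie between subjects, between visits and between scans. At five visits the true variance of the mean is p_s/20 + p_v/100 + p_e/300; the naive scan-level variance is 1/300. Coverage is 2Φ(1.96 × √(naive/true)) − 1.

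- p_s = 0.1, p_v = 0: true = 0.005 + 0.003 = 0.008; coverage 79%.
- p_s = 0.5, p_v = 0.2: true = 0.025 + 0.002 + 0.001 = 0.028; coverage 50%.
- Visit means, with naive variance (p_s + p_v + p_e/3)/100: 66–86% by simulation over p_s = 0.1–0.5 and p_v = 0 or 0.2.
- A t interval on the 20 subject means covers about 95% throughout.

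**Limits as point estimates.** The pooled SD is 0.98–1.00 of the true SD with 20 subjects, so clustering alone hardly moves the limits. The pair unit does. Single-scan limits exceed visit-mean limits by 1/√(p_s + p_v + p_e/3), from 1/√0.8 = 1.12 to 1/√0.4 = 1.58.

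**The case against.** The strongest reply is that the plan does not rest on pooled r. Bland-Altman limits, change-from-baseline summaries and subject listings are also planned. In the main model these expose both non-tracking devices: A by its SD of change (58 against about 200 mL/min for Duplex), and C by wider limits (±46% against ±36% for B). This stands. A reader might infer that the planned outputs would let a non-tracking device pass; the documents and these figures do not support that. What remains is narrower: none of these outputs measures whether the two methods change together in the same patient, and no acceptance limit is stated against which ±46% would be judged.

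It is also fair that the high pooled r depends on most variance lying between patients. During maturation the change within a patient may be large, and the effect then shrinks.

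A reader might infer that the removal rule fails when only some of a visit's Duplex flow scans pass. It does not: the rule works by data point, so failing values leave with their partners and passing ones stay. Only the matching is unstated.

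A reader might extend the tracking argument to 11.2.8.2. There both readings come from the same image, so the pair is clear, and the tracking figures above do not apply. Only the basis of any interval remains open.

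Finally, the plan specifies no interval, does not exclude a repeated-measures method, and allows additional analyses. True, but that allowance neither names a method nor defines the pair.

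**Conclusion.** The point holds in a limited form. Section 11.2.8.1 leaves the unit of pairing open, neither section names a subject term, and the pooled correlation cannot separate differences between patients from tracking within one. With 69–88% of true variance between subjects, pooled r barely separates the two kinds of device while within-subject r separates them clearly; with 30–50% the pooled figure is less misleading. All of this rests on assumed variances. That pooled r mixes the two sources does not depend on them, but the size does.

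The pooled limits are sound as point estimates. The loss of coverage applies only if an exploratory interval is reported and pairs are treated as independent. A reader might infer that the feasibility conclusion is at risk. It is not: the comparison is observational, section 11.1 sets no hypothesis, and no primary endpoint, sample size or decision rule depends on it. The consequence is modest, but the remedy is cheap enough to be worth making.

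**What to change.** 1. In 11.2.8.1, state the pair unit: matched single scans, or visit means of the scans that pass the quality check. Single-scan limits describe one device reading and visit-mean limits describe an average of three, so the choice should follow the intended use. State how EchoSure scans are matched when some of a visit's Duplex flow scans fail.
2. In 11.2.8.1, use repeated-measures Bland-Altman on percent difference with a random subject effect, plus visit within subject if single scans are used. In both 11.2.8.1 and 11.2.8.2, base any reported interval on the subject, for example a t interval on subject means for bias.
3. In 11.2.8.1, report a within-subject (repeated-measures) correlation beside the pooled Pearson r.

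The cost is a few sentences of text and modest programming, with no new data. Any intervals reported will be wider. For illustration, with an assumed difference SD of 25 percentage points and 300 scans, the naive half-width for bias is 1.96 × 25/√300 = 2.8 points, against 4.6 to 8.6 points on the subject basis over the variance shares used above.

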11.2.8.3 Time to Radiographic Maturation

Time to radiographic maturation is defined as the number of days from baseline procedure to date of radiographic maturation (date of ultrasound imaging).

Radiographic maturation is defined as fistula diameter \geq 5mm, fistula flow \geq 500 mL/min as assessed by physician based on ultrasound imaging and adjudicated by CEC.

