Medical History and Most Recent Kt/V, CBC, Serum chemistry, Calcium, Phosphorous, Magnesium, Total Protein, Albumin, PTH	х			х	х	х	х	х	х	х	х	х	х	х
Relevant Medications	x			х	х	Х	х	х	x	х	х	х	х	X
Physical Examination / Vital Signs	х	х	х	х	x	х	x	x	x	х	х			
Fistula Creation		x												
EchoMark LP Implantation		x												

Sonavex, Inc.	EchoMark/EchoSure System Feasibility Study Synopsis													
External EchoMark Measurements			Х	Х	х	Х	Х	Х	Х	Х	Х			
Duplex Scans	Х		Х	Х	Х	Х	Х	Х	Х	Х	Х	Х	Х	Х
EchoSure Scans*			X	Х	Х	Х	Х	Х	X					
Cannulation Log, including attempts				Х	Х	Х	Х	Х	х	Х	Х			
AE Monitoring		Х	X	Х	Х	Х	Х	Х	Х	Х	Х	Х	Х	Х
End of Study														Х

** Note: The monthly EchoSure scans will be suspended after the 120 day (4 month) visit or once radiographic maturation is achieved, whichever is longer. Patients will continue to be followed monthly with physical examination, Duplex, and AE monitoring until the 180-day timepoint. If radiographic maturation is never achieved, patients will be followed until either the fistula is abandoned, or the patient reaches the 180-day timepoint. The 180-day timepoint is meant to assess patency via Duplex and is meant for AE monitoring.

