7.12 EchoMark Explantation

If the EchoMark is removed, the subject will be followed until the event is resolved. A case report form will be completed to track the reasoning, procedure details, and outcomes. The subject will be monitored with the institution's standard of care, including physical exam and possibly ultrasound. The event will be tracked until the symptoms are resolved and the subject will exit the study.

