11.2.8.4 Time to Clinical Maturation

Time to clinical maturation is defined as the number of days from baseline procedure to date of clinical maturation (first date of 4-week window with 75% successful 2 needle cannulation).

Clinical maturation is defined as 75% of dialysis sessions with 2 needle cannulation for 4 weeks.

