11.2.10 Handling of Missing Data

Data will only be absent from analyses of study outcomes in the event that they were not available for collection. In general, missing values in any of the endpoints will not be inputted when summarizing these endpoints using descriptive statistics.

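### No time-to-event method is given for time to maturation, so under the general rules the mean and median would describe only subjects who matured and be biased toward short times

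*Combined protocol and SAP*

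**What the plan says.** Section 11.2.8.3 defines the radiographic time: "Time to radiographic maturation is defined as the number of days from baseline procedure to date of radiographic maturation (date of ultrasound imaging". Section 11.2.8.4 does the same for the clinical time: "Time to clinical maturation is defined as the number of days from baseline procedure to date of clinical maturation". Both sections stop at the definition. The methods that remain are the general ones:

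- Section 11.2.1: "Descriptive statistics will be used to present the data and to summarize results".
- Section 11.2.8, for continuous variables: "results will be summarized with the with the numbers of observations, means, medians, standard deviations, minimums, and maximums".
- Section 11.2.10: "In general, missing values in any of the endpoints will not be inputted when summarizing these endpoints using descriptive statistics".

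Kaplan-Meier estimation, cumulative incidence, censoring and competing events are not mentioned anywhere in the documents.

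Subjects without a maturation date are foreseen. The note under Table 1 (Schedule of Events) says: "If radiographic maturation is never achieved, patients will be followed until either the fistula is abandoned, or the patient reaches the 180-day timepoint". Section 7.11 covers abandoned fistulae. Section 7.12 covers explantation, after which follow-up ends: "The event will be tracked until the symptoms are resolved and the subject will exit the study". Sections 10.2 and 10.3 cover withdrawal and loss to follow-up.

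Sections 11.2.8.5 and 11.2.8.6 report the percentage who mature as separate endpoints. Section 11.2.4 sets the observational analysis sample as all enrolled subjects with a successful implant.

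**The concern.** A time defined as days to a date exists only for subjects who have the date. If it is summarised like any other continuous variable and missing values are left out, the summary conditions on success. A median computed this way does not respond to failure: 20 of 20 maturing and 10 of 20 maturing can give the same number. Subjects whose follow-up ends while they are still maturing are lost as well, and these tend to be the slow ones.

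What is at stake is a descriptive figure that a reader may take as the time a typical implanted subject needs, when it is the time among those who succeeded. Section 11.2.9 also plans an interim analysis at the last subject's 90-day visit and does not say which endpoints it covers. If these times are included, subjects still maturing at that date would be left out in the same way.

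**Working it through.** **Inputs.** Maturation percentages come from the comparison table in Section 3.5: 83.3% of 30 and 73.5% of 34 in prior device experience, and 64% in the national cohort of 45,087. The plan gives no distribution of time to maturation, so the shapes below are assumptions.

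**The plan's own figure.** 83.3% of 30 is 25/30, and 73.5% of 34 is 25/34. The exact (Clopper-Pearson) 95% interval for 25/30 is 65.28% to 94.36%, which reproduces the stated 65.3% to 94.4%.

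**Direction.** Let p be the proportion of all implanted subjects who mature during complete follow-up, and G the distribution of times among them. Cumulative incidence over all subjects is p × G(t). It reaches one half where G(t) = 0.5/p. The achiever-only median is where G(t) = 0.5. Since 0.5/p is at least 0.5, the achiever-only median can never be the longer of the two.

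- p = 0.833: 0.5/0.833 = 0.600, the 60th percentile of achievers
- p = 0.735: 0.5/0.735 = 0.680, the 68th percentile
- p = 0.64: 0.5/0.64 = 0.781, the 78th percentile
- p below 0.5: median not reached

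This step needs no assumption about shape.

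**Size, shape A (assumed).** Exponential times with p reached by day 150. Rate r = −ln(1 − p)/150; all-subject median = ln 2/r; achiever median = −ln(1 − p/2)/r.

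**Size, shape B (assumed).** Achiever times log-normal with median 90 days and log-SD 0.6. All-subject median = 90 × exp(0.6 × z), where z is the standard normal quantile at 0.5/p.

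| p | A: all vs achievers (days) | A: gap | B: all vs achievers (days) | B: gap |
|---|---|---|---|---|
| 83.3% | 58.1 vs 45.1 | 13.0 | 104.8 vs 90 | 14.8 |
| 73.5% | 78.3 vs 51.7 | 26.6 | 119.2 vs 90 | 29.2 |
| 64% | 101.8 vs 56.6 | 45.2 | 143.4 vs 90 | 53.4 |

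The gap runs from 13 to 53 days, about 2 to 8 weeks. The relative shortening depends on the shape: at 73.5% it is 1 − 51.7/78.3 = 34% under A and 1 − 90/119.2 = 24.5% under B.

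**Ties at visit dates.** Take 20 subjects of whom 15 mature, with times recorded at visits. The achiever median is the 8th ordered time; the all-subject median is the 10th (10/20 = 50%).

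- Times 30 (×3), 60 (×4), 90 (×4), 120 (×2), 150 (×2): 8th = 90 and 10th = 90, a tie.
- Times 30 (×2), 60 (×5), 90 (×2), 120 (×3), 150 (×3): 8th = 90 and 10th = 120, a gap of 30 days.

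**The case against.** The strongest reply is that the plan nowhere says it will analyse achievers only. The continuous-variable rule in Section 11.2.8 names flow, depth and diameter as examples and goes on to change from baseline, which means nothing for a time to event. Section 11.2.10 concerns data that could not be collected, and a fistula seen not to mature is an observed outcome. Section 11.2.4 puts every implanted subject in the sample. All of this is fair, and a reader who concludes that the plan prescribes an achiever-only analysis goes further than the text. What stands is that no other method is offered, and a subject without a date has no value to enter into a mean or median.

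Second, the success rates, the reported number of observations and the subject listings in Section 11.2.1 let a reader see how many subjects are behind the figure. That stands as mitigation, but it does not correct the figure.

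Third, the illustrations are weakly anchored. The day-150 horizon is not in the documents, and Section 3.5 speaks of average maturation of over 6 months and of 6 to 9 months. The 73.5% comes from a group in which 14.7% had no outcome yet, so it is not a maturation probability by any fixed day. This stands too: a reader might take 34%, or any single row of the table, as the bias expected in this trial, and the documents do not support that.

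Finally, a reader might infer that a device with more failures would look faster than a competitor. The trial has one arm, no pre-specified null hypothesis (Section 11.1) and no decision rule tied to these times, so no such comparison is planned.

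**Conclusion.** The concern holds as a gap in specification with a known direction. Followed as written, the general rules give achiever-only times that cannot have a longer median than the all-subject estimate and will usually have a shorter one. The direction follows from the definitions. The size, roughly 2 to 8 weeks at maturation percentages of 83.3% to 64%, rests on two assumed shapes and on percentages from other cohorts, and it can be zero when times cluster at visits. Severity is low to moderate: the endpoints are observational, the study is a descriptive feasibility trial of up to 20 subjects, and the success rates already show how many did not mature.

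**What to change.** In Sections 11.2.8.3 and 11.2.8.4, add the following:

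- Estimate the cumulative incidence of maturation in all implanted subjects (the Section 11.2.4 sample), with abandonment, explant and death as competing events. Do not use Kaplan-Meier with these events censored, since that overstates maturation.
- Censor other subjects at the last assessment at which maturation could be determined.
- Report the median with a 95% confidence interval, or state that it was not reached.
- Report cumulative maturation at the scheduled visits. For radiographic maturation, go through day 150: the Duplex lists in Sections 7.8 and 7.9 do not include fistula flow and diameter, so a first maturation after that may not be ascertainable. For clinical maturation, go through 12 months, using the cannulation log in Table 1.
- State that radiographic dates are known only to the visit at which imaging was done.
- Label any achiever-only mean or median as such and give its n.

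The cost is a few lines of text and a little standard analysis, with no new visits, data or subjects. The downside for the sponsor is that the reported median may be longer or not reached.
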